6.1 MODIFIED GINGIVAL INDEX, LOBENE ET AL (1986)

Full mouth gingival scores shall be visually assessed by segmenting marginal and papillary units, 6 sites per tooth: distobuccal, buccal, mesiobuccal and distolingual, lingual, mesiolingual surfaces. The last tooth in each quadrant will not have a distal site. Gingival inflammation shall be recorded at each site on a scale of 0 to 4.

0 = absence of inflammation;

1 = mild inflammation or with slight changes in color and texture but not in all portions of gingival marginal or papillary;

2 = mild inflammation, such as the preceding criteria, in all portions of gingival marginal on papillary;

3 = moderate, bright surface inflammation, erythema, edema and/or hypertrophy of gingival marginal or papillary;

4 = severe inflammation: erythema, edema and/or marginal gingival hypertrophy of the unit or spontaneous bleeding, papillary, congestion or ulceration.

6.2 PROBING DEPTH (PD)

Linear distance from the gingival margin (GM) to base of the pocket. If a PD reading falls between two millimeter readings, the rule shall be to round down and the lower of the two readings will be recorded.

6.3 BLEEDING ON PROBING (BOP)

Presence or absence of bleeding to manual probing recorded as a dichotomous variable.

0- No bleeding within 10 seconds after probing.

1- Bleeding within 10 seconds after probing.

6.4 CLINICAL ATTCHMENT LEVEL (CAL)

Linear distance from the cemento-enamel junction (CEJ) to base of the pocket. If a CAL reading falls between two millimeter readings, the rule shall be to round down and the lower of the two readings will be recorded.

6.5 RADIOGRAPHIC ANALYSIS

Cone Beam Computed Tomography (CBCT) will be performed following screening and at 6 months post-extraction prior to implant placement. CBCT will be used for pre-surgical planning for both the tooth extraction and implant placement. Hard tissue linear measurement analysis will be performed to compare ridge remodeling (baseline vs. 6-month healing). CBCT images will be analyzed by non-contact reverse

engineering system (Geomagic software). Fickl and collaborators demonstrated in an animal study the reliability of using this software to measure the tissue alterations after tooth extraction (Fickl, Zuhr et al. 2008).

For superimposition of the original DICOM data (Digital Imaging and Communications in Medicine) of the two CBCT scans, a computer-assisted superimposition will be done in selected areas of the data set, where no changes had taken place during the 6 months (e.g. the cranial base in the maxilla or the lower border and angle in the mandible respectively). By this step, the two data sets will be aligned and manually checked for perfect match. Subsequently, the measurements will be made at baseline and at 6 months using the same reference points and lines. To set a reference, the most apical point of the extraction socket will be defined in the baseline image and two reference lines will be subsequently drawn. The vertical reference line will be drawn in the center of the extraction socket crossing the apical reference point. The horizontal reference line will be drawn perpendicular to the vertical line crossing the apical reference point. The following measurements with respect to these reference points and lines will be performed in the center of the extraction socket:

- Thickness of the buccal bone plate at three levels (1mm, 3mm, and 5mm below the lingual bone crest).
- Height of the alveoli at the mid-buccal and mid-lingual aspect.
- The horizontal ridge width measured at three levels (at -1mm, -3mm, -5mm) below the most coronal aspect of the crest.
- Linear changes overtime will be assessed based on the measurements performed at baseline and at 6 months.

[figure not shown]

Figure 3. CBCT slice section. HW-1 (at -1mm), HW-3 (at -3mm), and HW-5 (at -5mm) represent measurements performed at 3 levels below the bone crest.

6.6 SOFT TISSUE ANALYSIS

Soft tissue volumetric analysis will be performed to compare the soft tissue healing between the test and control groups. Images captured with an intra-oral scanner (Trios, 3Shape) collected at baseline, week-1, week-2, week-4, month-3, and month-6. Soft tissue volumetric analysis will be performed to compare soft tissue ridge remodeling. STL files originated from intra-oral scanning images will be analyzed by non-contact reverse engineering system (Geomagic Qualify, Raindrop Geomagic, Research Triangle Park, NC, USA). A precision analysis study determined that surface reconstruction on Geomagic Qualify software provides a reliable analysis with a maximum deviation of 0.06mm, standard deviation of 0.003mm, and an average error of 0.002mm (Wang 2014). For superimposition of the original STL data (Stereolithography) of the intra-oral scans, a computer-assisted superimposition will be done in selected areas of the data set, where no changes had taken place during the 6 months (e.g. incisal edges or occlusal surfaces of teeth not included in the treated area). By this step, the data sets will be aligned and manually checked for perfect match. Volumetric changes overtime will be assessed based on the measurements performed baseline, week-1, week-2, week-4, month-3, and month-6 by subtraction analysis and expressed in percentage values.

7.0 STATISTICAL ANALYSIS

Descriptive statistics (means and standard deviations for continuous variables and frequencies for categorical variables) will be produced for vital signs, demographic characteristics, medical history and clinical variables, both overall, and for each of the two groups of study participants. Summaries of clinical variables will be presented at baseline and at study exit. Adverse events (including onset, duration, treatment, outcome and suspected causality) and reasons for withdrawals will be listed and summarized.

A power analysis was performed using a statistical power calculator (SAS Power Procedure, Cary, NC). This study will have a sample size of 24 subjects, 12 in each of the two groups. We will have at least 90% power (with a Type I error rate of 5%) to detect a difference of 2.5mm in the horizontal ridge width measured at 3mm below the most coronal aspect of the crest, assuming a standard deviation of 1.6mm, as determined by a previous study (Jung, Philipp et al. 2013). This power calculation takes into account the estimated 10% of subjects drop out. A “p” value of less than 0.05 will be considered statistically significant.

For soft tissue analysis, the primary outcome was the within-participant difference between the linear and volume changes at the test and control groups. These differences were measured in each participant prior to surgery, as well as 3 and 6 months after surgery, leading to a series of three longitudinal differences for each participant. For each group, the differences at all three time points were analyzed simultaneously using a linear mixed model (LMM), in which the actual linear and volume measures were modeled as a function of time (categorical), treatment group, and the interaction of time and treatment, while accounting for the repeated measures on each participant with a random participant effect. Given that both time and treatment are categorical, our approach was a generalized version of repeated measures ANOVA, as our LMM allowed for differing variability in linear and volume measures at each time point. Within each LMM, we also tested for a difference between the two treatment groups with respect to the overall time pattern in linear and volume measures. Due to the exploratory nature of the analysis, no Bonferroni correction for multiple testing was applied. Statistical significance was defined as a p -value < 0.05 .

For hard tissue analysis, to test the working hypothesis of systematic differences between the treatment groups, a two-sample equal variance student t-test with a two-tailed distribution was performed comparing the two groups for each of the linear measurements as well as for the volumetric analysis. Statistical significance was defined as a p -value < 0.05 .

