3.0 STUDY DESIGN

[figure not shown]
This study will be a randomized clinical trial involving a total of 24 subjects. We propose to recruit subjects into 2 groups: 1) Extraction treated with xenograft bone substitute (BioOss Collagen®) + collagen dressing (HeliPlug®), 2) Extraction treated with xenograft bone substitute (BioOss Collagen®) + 3D-collagen matrix (Mucograft Seal®). All subjects recruited will have already been approved and treatment planned for extraction + implant placement by non-study personnel to avoid any potential conflict of interest. All subjects will have radiographs that show the tooth planned for extraction. Each subject will be eligible for only 1 tooth extraction + dental implant rehabilitation. After tooth extraction, subjects will receive a standard site preservation therapy consisted with xenograft bone substitute + collagen dressing or the alternative site preservation therapy consisted with xenograft bone substitute + 3D-collagen matrix. After the conventional 6-month healing period, subjects will receive a dental implant in the previous extracted site. During the dental implant procedure, a 2x5mm bone core biopsy + a 2mm gingival biopsy will be obtained from the implant site.

Biopsy samples will be stored for future histological and histochemical analysis. After dental implant placement, all subjects will receive a healing abutment for soft tissue healing prior to implant restoration.

During the 6-month healing time after tooth extraction and site preservation therapy, subjects will return at week-1, week-2, week-4, month-3, and month-6 for intra-oral scanning for soft tissue volumetric acquirement. Subjects will receive a Cone beam computed tomography (CBCT) prior to extraction for the baseline hard-tissue volume measurement and appropriate extraction planning and at 6-month post-extraction for volumetric measurement and appropriate implant treatment planning.

Hard tissue analysis will be performed to compare linear ridge remodeling (baseline vs. 6-month healing). CBCT images will be analyzed by non-contact reverse engineering system (Geomagic software). Soft tissue volumetric analysis will be performed to compare the soft tissue healing between BioOss Collagen + Mucograft Seal and BioOss Collagen + Collagen Dressing. Images captured with an intra-oral scanner (Trios, 3Shape) collected at baseline, week-1, -2, -4, month-3, and month-6.

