4.1 INCLUSION CRITERIA

- † Subjects must be adult males or females age 18 to 80 years (inclusive).
- † Subjects must be able and willing to follow study procedures and instructions in English.
- † Subjects must have read, understood and signed an informed consent form in English.
- † Subjects must have a maxillary premolar, canine, lateral incisor, or central incisor with a restorative or periodontal hopeless prognosis (Kwok and Caton 2007), in which an implant is indicated without any sinus lift required.
- † Subjects undergoing implant placement should be in adequate periodontal health prior to implant placement. This includes having probing depth ≤ 4 mm for all remaining teeth at the same quadrant of the proposed implant placement. Patients with periodontal probing sites with probing depths of up to 5 mm may also be included if bleeding on probing in these sites is absent. Each subject should be considered to be periodontally stable prior to the implant surgery.

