4.4 SUBJECT IDENTIFICATION

At screening, participants will be assigned a 3-digit counter/screening number by the study center (001, 002, etc.). At treatment baseline/series, each subject will receive a unique 4-digit study number (1001, 1002, etc.) that will identify their group status in the study. Participants who do not complete the study will be replaced until 24 participants have completed the study.

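### Hard-tissue outcomes are compared without adjusting for the baseline value the trial already measures; ANCOVA would remove the linear effect of chance baseline imbalance and usually narrow the interval

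*Combined protocol and SAP*

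**What the plan says.** The hard-tissue paragraph of section 7.0 (Statistical Analysis) plans "a two-sample equal variance student t-test with a two-tailed distribution was performed comparing the two groups for each of the linear measurements" and extends the test to the volumetric analysis. It names no covariate. The linear mixed model earlier in section 7.0 is confined to soft tissue.

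Baseline values exist for every hard-tissue outcome. Section 6.5 (Radiographic Analysis) states that "the measurements will be made at baseline and at 6 months using the same reference points and lines". Section 3.0 (Study Design) schedules a CBCT "prior to extraction for the baseline hard-tissue volume measurement".

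The response variable is not stated. Section 6.5 says "Linear changes overtime will be assessed based on the measurements performed at baseline and at 6 months", and section 3.0 likewise speaks of comparing remodelling between baseline and 6 months, so change is the likelier response. The hard-tissue paragraph of section 7.0 does not confirm this.

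The power statement in section 7.0 concerns a 2.5 mm difference in ridge width 3 mm below the crest, "assuming a standard deviation of 1.6mm, as determined by a previous study". It does not say whether this is the SD of change or of month-6 width.

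**The concern.** Section 4.1 admits sites of different natural width: "Subjects must have a maxillary premolar, canine, lateral incisor, or central incisor". Section 3.2 allocates 12 and 12 by drawing slips, without stratification. In a trial this small, baseline ridge width can differ appreciably between arms by chance.

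An unadjusted test does not deal with that. A test on the month-6 value ignores the imbalance. A test on change subtracts the whole baseline difference, which is right only if the slope of month-6 width on baseline width is 1. Otherwise part of the baseline difference remains in the estimated treatment effect. Horizontal ridge width is the outcome on which the trial is powered, so its main hard-tissue result is exposed.

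The background in section 1.2 gives a mild reason to doubt a slope of 1. Twelve-month width losses of 6.1 mm (50%) overall and 4.9 mm (45%) at premolars imply starting widths of about 12.2 mm (6.1/0.50) and 10.9 mm (4.9/0.45), so the wider group lost more millimetres. These are literature averages and not the trial's treatments, so they are only illustrative.

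**Working it through.** **Inputs from the documents.** SD 1.6 mm, difference 2.5 mm, two-sided 5% level (section 7.0). Completers: 24, because section 4.4 says "Participants who do not complete the study will be replaced until 24 participants have completed the study"; taken as n = 12 per arm, N = 24.

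**Assumed, not in the documents.** Correlation rho between baseline and month 6, shown at 0.3, 0.5 and 0.7; ratio k = baseline SD / month-6 SD, shown at 1 and 0.7; normal data with a linear relation.

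**1. The plan's own figure.** Noncentrality 2.5 / (1.6 × √(2/12)) = 3.83 on 22 df gives power 95.5%. With 11 per arm it is 93.6% and with 10 it is 91.0%. The claim of at least 90% after 10% dropout therefore holds.

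**2. Chance imbalance.** The SD of the baseline mean difference is √(2/12) = 0.41 baseline SDs. The probability that it exceeds 0.5 SD in either direction is 22%.

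**3. Bias given an imbalance of 0.5 baseline SD.** The slope is b = rho/k. A t-test on change is biased by (b − 1) × 0.5 × baseline SD. If 1.6 mm is the SD of change, the baseline SD is k × 1.6 / √(1 + k² − 2·rho·k).

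| rho | size of bias, k = 1 | size of bias, k = 0.7 |
|---|---|---|
| 0.3 | 0.7 × 0.5 × 1.35 = 0.47 mm | 0.31 mm |
| 0.5 | 0.5 × 0.5 × 1.60 = 0.40 mm | 0.18 mm |
| 0.7 | 0.3 × 0.5 × 2.07 = 0.31 mm | 0 (slope = 1) |

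At k = 1 this is 19% to 12% of the 2.5 mm design difference. If month-6 width is tested and 1.6 mm is its SD, the bias is rho × 0.5 × 1.6 = 0.24, 0.40 and 0.56 mm.

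**4. False-positive rate when the imbalance exceeds 0.5 SD** (simulation, 200,000 trials with no treatment difference per setting).

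| rho | t-test on change, k = 1 | t-test on change, k = 0.7 | t-test on month-6 value | ANCOVA |
|---|---|---|---|---|
| 0.3 | 12% | 8% | 7% | 5% |
| 0.5 | 10% | 6% | 10% | 5% |
| 0.7 | 8% | 5% | 15% | 5% |

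Over all randomisations every method averages 5%. In the other 78% of trials the t-test on change is conservative: at k = 1, about 3% at rho 0.3 and 4% at rho 0.7.

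**5. Precision.** The unadjusted 95% CI half-width is t(0.975, 22) × 1.6 × √(2/12) = 2.074 × 1.6 × 0.408 = 1.35 mm. ANCOVA has 21 df (t = 2.080) and an average inflation of 1 + 1/(N − 4) = 1.05 for estimating the slope. Its half-width is 2.080 × 1.6 × √(V × 1.05 × 2/12), where V is the variance ratio: (1 − rho²)/(1 + k² − 2·rho·k) against change, or 1 − rho² against month-6 width.

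| rho | 1.6 mm is SD of change, k = 1 | same, k = 0.7 | 1.6 mm is SD of month-6 width |
|---|---|---|---|
| 0.3 | 1.12 | 1.28 | 1.33 |
| 0.5 | 1.21 | 1.36 | 1.21 |
| 0.7 | 1.28 | 1.39 | 0.99 |

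**6. Where the precision gain ends.** At k = 1 the average gain disappears above rho of about 0.89 (against change) or below about 0.23 (against month-6 width). The largest average loss, when V = 1, is (2.080 × √1.05)/2.074 − 1 = 2.8%.

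**The case against.** The best case for leaving the plan alone is that nothing in it is wrong: the t-test is valid, its error rate averages 5%, and the power target is met. That stands, and it makes this a recommended improvement rather than the correction of an error.

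The size of the gain also rests on a correlation that the documents do not give. Repeat measurements on superimposed scans could correlate more strongly than 0.7. With k = 1, rho of 0.8 gives a half-width of 1.32 mm and a conditional false-positive rate of about 7%; rho of 0.9 gives no gain in width and a rate of about 6%. At k = 0.7 and rho 0.7 a t-test on change has no conditional bias at all. So 12% is the top of the range shown for the test on change, not a typical value.

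Three further points stand in part. Section 7.0 describes the tests in the past tense, so the arms may already have been compared. The adjustment covers one baseline measure and not tooth type, which is one source of the imbalance. The calculations use the SD for one ridge-width level; linearity is less assured for buccal plate thickness, which cannot fall below zero.

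None of this reverses the conclusion. The possible loss is bounded at about 3% of average interval width, and the possible benefit is larger under either reading of the response variable.

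**Conclusion.** The concern holds. The hard-tissue comparison ignores a baseline value that is collected for every outcome. In the roughly one trial in five with an imbalance above 0.5 SD, a t-test on change is biased by 0.31 to 0.47 mm at an imbalance of exactly 0.5 SD, and its false-positive rate across those trials is about 8% to 12% (1.6 mm as SD of change, equal SDs, rho 0.3 to 0.7). ANCOVA keeps about 5%. The expected half-width falls by 5% to 17% in the same setting. These sizes depend on the assumed rho and SD ratio, and with a smaller baseline SD both the bias and the precision gain can vanish. This is a matter of conditional bias and precision. It is not a sample-size error and does not make the planned test invalid.

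**What to change.** In the hard-tissue paragraph of section 7.0:

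- State that the response is change from baseline to month 6.
- For each linear measure, make the main analysis an ANCOVA with treatment as factor and that measure's baseline value as covariate. Do the same for hard-tissue volume with baseline volume.
- Report the adjusted difference with its 95% CI, and keep the unadjusted t-test on change as a sensitivity analysis.
- Fix the model before any unblinded comparison of the arms. If the arms have already been compared, report ANCOVA as a labelled supplementary analysis instead.

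With change or month-6 value as the response and baseline as covariate, the adjusted treatment difference is the same, so this choice does not affect the main result. It does affect the sensitivity t-test, which is why it must be stated.

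The cost is a few lines of text and one degree of freedom. No new data or visits are needed, and the worst case is an interval about 3% wider on average.

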8.0 SAFETY EVALUATIONS

8.1 DATA COLLECTION AND ANALYSIS

Data collection will be conducted on desktop and laptop computers located chairside in the GO Health Center,

UNC-School of Dentistry. These computers are stored in a locked area, and are password protected. Daily data backup is performed on a password protected network which moves the data to a secure server. This prevents any inadvertent breach in confidentiality of the data collected. Personal identifying information is stored in a separate secure database from the research data. Hard copies of the data sheets are kept in a locked office. Research samples will be identified only by unique numbers assigned to the participants. The specimens will

be coded. Linkage to the code will be retained by the study coordinator in a combination-locked workspace accessible only by study personnel.

8.2 VITAL SIGNS MEASUREMENTS

Vital signs (pulse, respiration, blood pressure) will be measured at each visit. At baseline height and weight will be determined. During test cylinder placement and removal standard clinical vital monitoring will be performed.

8.3 EXAMINATION OF THE ORAL CAVITY

At each study visit, an evaluation of patients' extra- and intraoral structures will be conducted. Each examination will include a survey of the face, lymph nodes, lips, buccal mucosa, floor of the mouth, tongue, hard and soft palates, gingiva, edentulous ridges and teeth. Findings will be recorded as normal or abnormal. Abnormal findings will be described with respect to onset, location, size (severity) and diagnosis. Standardized dental exam will be conducted by a calibrated dentist or hygienist with experience in conducting periodontal exams. Even though discomfort is minimal, each person's tolerance level can be different. The consent form explains to the subject they can stop the dental exam at any time. The instruments and materials used for the screening exam are a periodontal probe, an examination mouth mirror, a dental explorer and 2"x2" gauze. These four items are sterilized in an autoclave for 30 minutes in 275 degrees Fahrenheit (as recommended per OSHA standards in sterilization of dental instruments). The examination package with these three items is opened immediately before the exam so that it remains sterile. The examiner wears a gown uses gloves and wears a mask. For radiographs, standard precautions including using the lowest dose possible and using a lead apron during the x-rays to minimize exposure.

8.4 PATIENT DEMOGRAPHICS AND MEDICAL HISTORY

At screening, the patient's age, sex, racial, and ethnic group, and smoking status will be recorded. In addition, the subject's medical history will be reviewed; concurrent medications will be recorded and height and weight will be measured. At every study visit medical history will be updated, weight will be measured; concurrent medications and infections will be reviewed.

9.0 CONDITION FOR DISCONTINUING PARTICIPANTS

Participants in this clinical study may be discontinued for any of the following reasons: 1) concurrent illness that would compromise immune response or healing; 2) protocol violations; 3) administrative reasons; 4) withdrawal of consent; or 5) poor healing response.

Subjects with dehiscence, fenestrated, or fractured labial/buccal with dehiscence, fenestrated, or fractured labial/buccal alveolar bone plate determined after baseline CBCT or after tooth extraction where more than 50% of the buccal bone height is not present. In this case, if the surgeon determines that guided bone regeneration (bone graft and membrane) is needed to repair the defect, it will be done at no cost to the subject, but the subject will be excluded from the study protocol. If after tooth extraction more than 50% of the buccal bone height is not present, the surgeon will perform guided bone regeneration (bone graft and collagen membrane) to repair the defect, it will be done at no cost to the subject, but the subject will be excluded from the study protocol.

Any subject presenting with healing response that in the judgment of the clinical provider may result in either infection, loss of osseous structure or soft tissue healing abnormalities to any of the surgical procedures, will have the graft material or dental implant removed immediately. If any healing problems arise, a second therapist not associated with the investigation will evaluate the patient to decide whether the subject should be exited or can continue. Moreover, each subject with poor tissue response or exited for any reason will be monitored until healing has resolved and appropriate care is provided to restore existing structures.

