1.4.2 FREE SOFT-TISSUE GRAFT OVER MINERALIZED BONE GRAFT

The placement of free soft-tissue graft to cover the augmented alveolar socket was introduced to minimize the soft tissue shrinkage, optimize aesthetical results of implant restoration and obtain a primary closure that may preserve the graft from bacterial infections and secondary graft failure (Stimmelmayer, Allen et al. 2010, Thalmeier, Hinze et al. 2010). The first attempt to cover the socket graft with an autogenous soft tissue implant was described by Landsberg and Bichacho in 1994 (Landsberg and Bichacho 1994). Nevins *et al.* suggested the use of soft tissue grafts to improve ridge topography after tooth extraction (Nevins and Mellonig 1994) and in combination with immediate implant placement (Landsberg 1997).

In 1999 Tal described the survival of circular connective tissue grafts placed over extraction sockets treated either with DFDBA or Bio-Oss. They found that the survival was not dependent on the adopted graft and that at 1 week 18/42 grafts were vital, 13/42 were partially vital and 11/42 were non-vital. Complete closure of all sockets occurred 4 weeks post extraction. The Authors noted that more often partially vital grafts maintained their vitality over the socket area more than on the graft margins; they concluded that the nourishment could be originated from plasmatic elements in the socket blood clot more than from vessels originating from the periphery of the graft (Tal 1999).

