8.1 HANDLING OF WITHDRAWALS

All participants prematurely discontinued from the study, regardless of cause will be encouraged and given the opportunity to be seen for a final evaluation. The reason(s) for withdrawal will be recorded in the CRF by the study coordinator and/or investigator.

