11.0 ADVERSE EVENTS

An adverse experience (AE) is any experience that suggests a significant hazard, contraindication, side effect, or precaution. With respect to human clinical experience, a serious adverse experience includes any untoward event that is fatal or life-threatening, is permanently disabling, requires or prolongs hospitalization, is a congenital anomaly, cancer, result of an overdose, or requires intervention to prevent permanent damage. In

the event of a serious adverse experience, the principal investigator or study coordinator must be contacted immediately by telephone. In the event that the principal investigator or study coordinator cannot be directly reached, a message must be left by voice mail within 24 hours of the incident.

All adverse events will be recorded although a distinction will be drawn between reactions normally experienced in conjunction with conventional periodontal therapy extractions and experiences not usually encountered. Unanticipated or possible related adverse events will be evaluated by open questioning throughout the trial. Examples of adverse events that may warrant subject removal from study participation include: infection, loss of primary stabilization, excessive inflammation, swelling, bleeding or pain. The onset, duration, treatment, and outcome of all such unanticipated adverse experiences must be recorded on the appropriate case report forms and reported within 7 business days to the Biomedical IRB. All anticipated and unrelated adverse experiences will be recorded on the appropriate case report forms.

The following definitions of severity should be used in the evaluation of AEs:

- Mild*: an AE that is easily tolerated and does not interfere with daily activities.
- Moderate*: an AE that is sufficiently discomforting so as to interfere with daily activities or receive interventional treatment.
- Severe*: an AE that prevents normal everyday activity.

The following definitions of relationship to implant surgery should be used in assessing the suspected causality of an AE:

- Probably Related*: there is a direct cause and effect relationship between the AE and the surgical procedure
- Possibly Related*: a direct cause and effect relationship between the surgical procedure and the AE has not been demonstrated, but is likely, possible, or cannot be ruled out, even if improbable

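### Subjects may be exited for poor healing or infection, need not be measured at month 6 and are replaced, so the month-6 comparison is partly selected towards well-healed sockets

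*Combined protocol and SAP*

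**What the plan says.** - **Grounds for exit.** Section 9.0 (Condition for Discontinuing Participants) says that participants may be discontinued for listed reasons, the last two being "4) withdrawal of consent; or 5) poor healing response". Section 11.0 (Adverse Events) adds: "Examples of adverse events that may warrant subject removal from study participation include: infection, loss of primary stabilization, excessive inflammation, swelling, bleeding or pain".
- **Treatment and exit decision.** Under section 9.0, a subject whose healing response worries the provider "will have the graft material or dental implant removed immediately". Where healing goes wrong, "a second therapist not associated with the investigation will evaluate the patient to decide whether the subject should be exited or can continue".
- **After exit.** Section 9.0 states that "each subject with poor tissue response or exited for any reason will be monitored until healing has resolved". Section 8.1 (Handling of Withdrawals) says that discontinued participants will be "encouraged and given the opportunity to be seen for a final evaluation". It gives neither content nor timing for that evaluation. No section requires the month-3 or month-6 intra-oral scan, or the month-6 CBCT, of an exited subject.
- **Replacement.** Section 4.4 replaces non-completers until 24 participants have finished.
- **Analysis.** Section 7.0 compares the arms on the CBCT measurements by a two-sample t-test and on soft tissue by a linear mixed model over baseline, month 3 and month 6. It defines no analysis set and no rule for missing values. It does list and summarise adverse events and reasons for withdrawal.
- **Masking.** Section 3.1 masks only the volumetric assessments.

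**The concern.** The plan does not separate stopping the randomised treatment (graft lost or removed) from leaving the study. A socket that becomes infected or heals badly may have done so because of what was placed in and over it, and wound healing is part of Aim 2. If such a subject is exited, the month-6 ridge measurement is not required and the place goes to someone else. Whether an endpoint is observed then depends on the outcome itself.

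If one covering led to more failed sockets than the other, that arm would lose some of its worst ridges and look better than it is. The providers who judge healing are not masked: the coverings and the suturing differ between arms (section 5.3, Visit 2). A measurement that was never taken cannot be recovered by a later choice of analysis set.

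**Working it through.** **1. The plan's power figure.** Inputs from section 7.0: difference 2.5 mm, SD 1.6 mm, two-sided 5% level, 12 per arm, 10% dropout. With the noncentral t distribution, power is 95.5% at 12 per arm, 92.4% at 11 versus 10, and 91.0% at 10 per arm. The stated figure of at least 90% reproduces. The problem is selection, not sample size.

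**2. Which analyses are exposed.** The t-test uses a baseline-to-month-6 CBCT comparison (section 6.5), so a subject without the month-6 CBCT drops out of it. The mixed model can keep a subject's earlier scans, but it is then valid only if data are missing at random given what was observed. Exit for poor healing puts that in doubt.

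**3. Scale.** The standard error of the difference is 1.6 × √(2/12) = 0.65 mm. Expected dropout for all reasons is 0.10 × 12 = 1.2 subjects per arm.

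**4. Shift if the worst healers of one arm exit.** The documents give no failure rate, so this rests on assumptions: a normal outcome with SD 1.6 mm, exits in one arm only, and exited subjects who are exactly the lowest values of 12. The expected lowest and second-lowest of 12 standard normal values are −1.629 and −1.116.

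- One exit: 1.629 × 1.6 / 11 = 0.24 mm. With a fresh replacement: 1.629 × 1.6 / 12 = 0.22 mm.
- Two exits: (1.629 + 1.116) × 1.6 / 10 = 0.44 mm. With replacements: (1.629 + 1.116) × 1.6 / 12 = 0.37 mm.

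Simulation of 1,000,000 arms agrees to two decimals. Since section 4.4 replaces non-completers, the replacement figures fit the plan better. One exit is then 0.22/0.65, about a third of a standard error, and 0.22/2.5, about 9% of the design difference. Two exits are 0.37/0.65 = 57% of a standard error and 0.37/2.5 = 15% of the design difference.

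**5. Shift under different failure rates.** Suppose instead that failed sockets lose L mm more width, that failure rates are fc (control) and ft (test), and that every failure exits and is replaced. The completers' difference then misses (fc − ft) × L:

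| fc / ft | L = 1.6 mm | L = 2.5 mm | L = 4 mm |
|---|---|---|---|
| 10% / 10% | 0 | 0 | 0 |
| 10% / 0% | 0.16 | 0.25 | 0.40 |
| 25% / 8.3% (3 v 1 of 12) | 0.27 | 0.42 | 0.67 |

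Reversing the rates reverses the sign, so the bias can favour either arm.

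**The case against.** The case against a strong version of this point is substantial, and most of it stands.

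- **Is the comparison limited to sockets that healed well?** A reader might infer so. The documents do not support it: both sections use permissive wording, and a therapist outside the investigation may let a poor healer continue. That therapist is not stated to be masked, but the rule means the selection is partial.
- **Are exited subjects abandoned?** No. They are monitored until healed, and reasons for withdrawal are recorded and summarised. This discloses the exits but does not supply the month-6 value.
- **Do the exits remove the very events the covering is meant to prevent?** Section 1.4.2 does speak of wanting to "obtain a primary closure that may preserve the graft from bacterial infections and secondary graft failure", but it describes free soft-tissue grafts, which neither arm receives. Section 1.4.3 calls the test matrix an alternative to such grafts and argues from volume preservation, clot stabilisation and tissue integration. It makes no claim about infection or graft failure.
- **Does every listed event cost month-6 data?** No. Loss of primary stabilisation appears to concern the implant, which is placed at Visit 8, after the month-6 CBCT and scan at Visit 7.
- **Are the magnitudes a worst case?** Yes. They place all exits in one arm and among its lowest ridge values, whereas pain, swelling or bleeding need not track ridge width. Both arms receive the same bone substitute, and nothing in the documents suggests different failure rates.

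What survives is that outcome-related exit, no required month-6 measurement and replacement act together, and the plan has no safeguard against the selection that results.

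**Conclusion.** The point holds in a limited form. Followed as written, the plan lets poor outcomes of the randomised treatment lead to exit, does not require the endpoint afterwards, and refills the place. The month-6 comparison, above all the t-test on CBCT measures, is therefore partly selected towards well-healed sockets.

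If the one or two worst healers of a single arm exit, that arm's mean moves by about 0.24 or 0.44 mm, or 0.22 or 0.37 mm with replacement. That is below one standard error (0.65 mm) and well below 2.5 mm, but not negligible with 12 per arm. With equal failure rates and losses in both arms, the shift in the difference is zero. The documents cannot say which situation will arise, and the trial as written would not measure it. This is a cheap improvement worth making, not evidence that the trial's result will be wrong.

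**What to change.** Leave the clinical rules on discontinuation and graft removal as they are, and change only what happens to the data.

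- **Sections 9.0, 8.1 (Handling of Withdrawals) and 11.0:** state that stopping study treatment or losing the graft does not end outcome collection. Unless consent to follow-up is withdrawn, keep the scheduled month-3 and month-6 intra-oral scans, and use the month-6 CBCT whenever it is taken for implant planning.
- **Sections 4.4 and 7.0:** state that a replaced subject is not dropped, and that all randomised and treated subjects are analysed in their assigned arm. Add a sensitivity analysis for failed sockets without month-6 data, since some CBCTs will still be missing.
- **Reporting:** tabulate exits, graft loss, infection and poor healing by arm. Label any scan from an early final evaluation with its actual time, not as month 6.

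The cost is amendment wording and a case report form page, since the visits and imaging are already planned for every subject. There are two downsides. Measurements after graft removal include the effect of later care, so section 7.0 should say that the comparison is of assigned treatment including that care. A few poor outcomes may also widen the interval slightly.
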